4.3 Study Duration

The expected duration of the study is 134 months, including a 56-month enrollment followed by 78 months of subject treatment and/or observation, including EP. The study is planned to conclude 78 months after the last subject is randomized.

5 TABLE OF EVENTS

Table 1 provides a detailed description of all study events or procedures by time point for each 28-day treatment cycle.

Table 1: Table of Events

Procedure	Screening ≤ 56 days prior to Randomization	Random- ization ^b	Double Blind Treatment Phase ^a						Follow- up ^a
			Cycles 1 – 2		Cycles 3 – 12		Cycles 13 and Beyond	Treatment Discon- tinuation ^c	
			Day 1 ^b	Days 8, 15, 22	Day 1	Day 15	Day 1		
Informed Consent	×	--	--	--	--	--	--	--	--
Inclusion and Exclusion Criteria	×	--	--	--	--	--	--	--	--
MDS Diagnosis, WHO Classification and IPSS Score	× ^d	--	--	--	--	--	--	--	--
RBC and Platelet Transfusion History	× ^e		--	--	--	--	--	--	--
Thrombocytopenia History	× ^f		--	--	--	--	--	--	--
Demographics and Medical History	×	--	--	--	--	--	--	--	--
Prior Treatment for MDS (and other malignancy, if applicable)	× ^g	--	--	--	--	--	--	--	--
Prior Medications	× ^h	--	--	--	--	--	--	--	--
Physical Examination	×	--	× ⁱ	--	×	--	×	×	--
Vital Signs (blood pressure, pulse, temperature, respiratory rate)	×	--	×	--	×	--	×	×	--
Body Weight Measurement	×	--	×	--	×	--	×	×	--
Height	×	--	--	--	--	--	--	--	--
ECOG Performance Status	×	--	× ⁱ	--	×	--	×	×	--
ECG – Local	× ^j	--	--	--	--	--	--	--	--
Urinalysis	× ^k	--	--	--	--	--	--	--	--

Table 1: Table of Events

Procedure	Screening ≤ 56 days prior to Randomization	Random- ization ^b	Double Blind Treatment Phase ^a						Follow- up ^a
			Cycles 1 – 2		Cycles 3 – 12		Cycles 13 and Beyond	Treatment Discon- tinuation ^c	
			Day 1 ^b	Days 8, 15, 22	Day 1	Day 15	Day 1		
Coagulation	x ^l	--	--	--	--	--	--	--	--
Coombs' Test (Direct/Indirect) - Local	x ^m	--	--	--	--	--	--	--	--
Reticulocyte Count - Local	x ⁿ	--	--	--	--	--	--	--	--
Serum EPO Level	x ^o	--	--	--	x ^o	--	--	--	--
Serum Ferritin ^p	x	--	x	--	x	--	x	x	--
Serum Transferrin Saturation (Fe/TIBC)	x	--	--	--	--	--	--	--	--
Hematology ^q	x	--	x ⁱ	x	x	x	x	x	--
Serum Chemistry ^r	x	--	x ⁱ	x	x	--	x	x	--
Pregnancy Testing (FCBP only) ^s	x	--	x	--	x	--	x	x	--
Assessing Adverse Events	After signing ICD and until 28 days after the last IP dose or until the last study visit, whichever period is longer.								
Monitoring for Progression to AML and Second Primary Malignancy	After signing ICD and until death, lost to follow-up, withdrawal of consent for further data collection, or study closure.								
Concomitant Medications, Therapy, and Procedures	--	From the date of randomization and until 28 days after the last dose of IP or until the last study visit, whichever period is longer							
Bone Marrow Aspirate and/or Biopsy (Biopsy mandatory at Screening)	x ^d	--	--	--	x ^t	--	x ^t	--	--
Peripheral Blood Smear									
Cytogenetic Testing									

Table 1: Table of Events

Procedure	Screening ≤ 56 days prior to Randomization	Random- ization ^b	Double Blind Treatment Phase ^a						Follow-up ^a
			Cycles 1 – 2		Cycles 3 – 12		Cycles 13 and Beyond	Treatment Discontinuation ^c	
			Day 1 ^b	Days 8, 15, 22	Day 1	Day 15	Day 1		
FACT-An and EQ-5D^x	--	--	×	--	×	--	×	×	--
Healthcare Resource Utilization	After signing ICD and until 28 days after the last IP dose or until the last study visit, whichever period is longer								
Randomization	--	×	--	--	--	--	--	--	--
IP Dispensation^y	--	--	×	--	×	--	×	--	--
IP Administration	--	--	Day 1 to Day 21 of 28-day treatment cycles ^z					--	--
IP Accountability	--	--	× ^{aa}	--	×	--	×	×	--
Transfusion Assessment^{cc}	--	--	After the date of randomization and until 28 days after the last dose of IP or until the last study visit, whichever period is longer						
Assessment of Bleeding Events^{dd}	--	--	×	×	×	×	×	×	--
IWG Response/Improvement^{ee}	--	--	--	--	× ^t	--	× ^t	--	--
Disease Status Assessment	--	--	--	--	× ^{ff}	--	× ^{ff}	×	--
Subsequent MDS Therapies	--	--	--	--	--	--	--	×	× ^{gg, hh}
Survival Follow-up	--	--	--	--	--	--	--	--	× ^{gg, hh}

Key: AML=acute myeloid leukemia; ECG=electrocardiogram; ECOG=Eastern Cooperative Oncology Group; EPO=erythropoietin; EQ-5D=EuroQol Group EQ-5D-3L; FACT-An=Functional Assessment of Cancer Therapy-Anemia; FCBP=female of childbearing potential; ICD=informed consent document; IP=investigational product; IPSS=International Prognostic Scoring System; IWG= International Working Group; MDS=myelodysplastic syndromes; RBC=red blood cell; WHO=World Health Organization.

- a. The study visit window for visit related assessments in the double-blind treatment phase is ± 3 days for Cycles 1 and 2; ± 7 days for Cycle 3 and beyond, unless noted otherwise for a particular assessment. **However, please note that in all circumstances a drug holiday of 7 days needs to be maintained for the treatment schedules of 300 mg and 200 mg for 21 days /28-day-cycle (14 and 21 days, respectively, for modified treatment schedules of 200 mg for 14 days/28-day-cycle and 7 days/28-day-cycle.** Study visits should also take into account the subject's IP supply. Only 1 cycle of IP will be dispensed to the subject on Day 1 of each cycle. Day 1 of Cycles 2 and beyond may be delayed from Day 28 of the prior cycle in order for subjects to recover from toxicity and meet criteria for re-treatment ([Section 8.2.5](#)). During follow-up, the study visit window is ± 7 days for visits scheduled monthly (including the follow-up visit 28 days after last dose if necessary) or ± 14 days for visits scheduled every 3 month. One cycle (one month) is considered as 28 days (ie, 4 weeks).
- b. First dose of IP in Cycle 1 should be administered within 3 days of randomization and can be on the same day of randomization.
- c. All subjects who have received at least one dose of IP should undergo Treatment Discontinuation procedures detailed in [Section 6.13](#) when treatment is discontinued. The reason for discontinuation will be recorded in the CRF and in the source document for all randomized subjects, regardless of whether they are dosed or not. Reasons for discontinuation are provided in [Section 12](#).
- d. MDS diagnosis, WHO classification ([Appendix A](#)), and IPSS risk classification ([Appendix B](#)) will be prospectively determined by independent central pathology and cytogenetics review, and applicable central laboratory results. Thus bone marrow aspirate and biopsy samples together with peripheral blood samples must be collected at screening as detailed in [Section 6.1.1](#). At all later time points a biopsy is only needed if adequate aspirate is not attainable. Blood samples at screening should be collected on the same day as the bone marrow aspirate/biopsy procedure. Instructions for submission of bone marrow slides, sample collection, processing, storage, and shipment procedures are provided in the study's Central Laboratory Manual.
- e. Red blood cell transfusion history must be available for the 56 days immediately preceding and including the date of randomization and platelet transfusion history must be available for the 56 days immediately preceding and including the date of randomization. Transfusion history data can be gathered during the 56-day screening period as detailed in [Section 6.1.2](#).
- f. Thrombocytopenia at baseline must be confirmed by two platelet counts that are $\leq 75 \times 10^9/L$ and ≥ 21 days apart. The second confirmatory platelet count must be obtained ≤ 14 days prior to randomization. At least one platelet count must be centrally analyzed within the 56 day screening period with results of $\leq 75 \times 10^9/L$; the second platelet count may be centrally or locally analyzed, with results that are also $\leq 75 \times 10^9/L$. If additional platelet counts are obtained during the interim period, these must also have been $\leq 75 \times 10^9/L$. If platelet counts within the interim period are $> 75 \times 10^9/L$, this would be acceptable only if associated with a platelet transfusion administered within 7 days prior to the date of the platelet count ([Section 6.1.3](#)).
- g. Prior Treatment for MDS includes all prior treatments for MDS regardless of discontinuation date of treatment as detailed in [Section 6.1.5](#).
- h. All medications taken in the 8 weeks (56 days) prior to randomization are to be collected on the appropriate Case Report Form (CRF).
- i. The assessment does not need to be performed if the screening examination was performed within 7 days of the first dose of IP in the treatment phase.
- j. Electrocardiogram will be performed locally at screening and whenever clinically indicated. The investigator will review and assess the results as detailed in [Section 6.1.9](#).
- k. Urinalysis is conducted at the central laboratory at screening and whenever clinically indicated as detailed in [Section 6.1.10](#).
- l. Coagulation is conducted at the central laboratory at screening and whenever clinically indicated as detailed in [Section 6.1.11](#).
- m. A direct or indirect Coombs' test at screening is performed at the local laboratory.
- n. The screening reticulocyte count is performed at the local laboratory.

- o. Ideally, the screening serum EPO level ([Section 6.1.14](#)) should be collected on the same day as a planned RBC transfusion, and should not be collected within 1 week after any RBC transfusion due to possible reduction of the serum level related to the hemoglobin level achieved after the last transfusion. Serum EPO level should also be tested on Day 1 of Cycle 6. However, if possible, the sample should not be collected within 1 week after any RBC transfusion due to possible reduction of the serum level related to the hemoglobin level achieved after the last transfusion. Therefore in the event that Day 1 of Cycle 6 would be scheduled within a week of a RBC transfusion, EPO sampling may be performed on Day 1 of the following cycle ([Section 6.7.7](#)). Serum EPO level is tested at the central laboratory.
- p. Serum ferritin level must be collected at screening, on Day 1 of Cycle 1, on Day 1 of every 3 cycles thereafter (eg, Day 1 of Cycles 4, 7, 10, 13, etc.) ([Section 6.6.6](#)), and at Treatment Discontinuation. Serum ferritin level is tested by the central laboratory.
- q. Hematology includes a complete blood count as detailed in [Section 6.1.17](#). Any or all laboratory assessments may be repeated more frequently if clinically indicated. All samples will be analyzed by the central laboratory. The samples are to be collected at screening and prior to IP administration as detailed in [Section 6.6.5](#), and at Treatment Discontinuation.
- r. Serum chemistry parameters are detailed in [Section 6.1.18](#). All samples will be analyzed by the central laboratory. Any or all laboratory assessments may be repeated more frequently if clinically indicated. The samples are to be collected at screening and prior to IP administration as detailed in [Section 6.6.5](#), and at Treatment Discontinuation.
- s. For females of childbearing potential (FCBP, please refer to [Section 6.1.19](#) for definition of FCBP) a medically supervised serum pregnancy test (conducted at the central laboratory or locally) is to be obtained and verified negative at screening ([Section 6.1.19](#)). During the treatment phase a serum or urine pregnancy test (investigator's discretion; sensitivity of at least 25 mIU/mL) is to be done within 72 hours prior to Day 1 of every cycle and at the Treatment Discontinuation visit ([Section 6.6.7](#)). Note that the screening pregnancy test can be used as the test prior to starting study therapy in the treatment phase if it is performed within the 72-hour timeframe. The subject may not receive IP until the investigator has verified that the result of the pregnancy test is negative.
- t. Day 1 of Cycles 3, 6, and 12 and every 6 months thereafter (eg, Day 1 of Cycles 18, 24, etc.). See [Section 6.7.3](#), [Section 6.10.1](#) and [Section 6.10.2](#) for detail.
■
■
■
■
- x. FACT-An and EQ-5D questionnaires must be completed prior to interaction with study personnel (when feasible) and prior to IP administration at the start of every Cycle, and at Treatment Discontinuation ([Section 6.8](#)). If blood is drawn in advance of Day 1 of a particular cycle or in advance of the treatment discontinuation visit, the questionnaires will still be completed at the first visit with the site staff at that particular cycle or treatment discontinuation visit.
- y. IP should only be dispensed on Day 1 of each treatment cycle after all Day 1 procedures have been completed and all IP from the previous cycle has been accounted for (where applicable). Only 1 cycle of IP will be dispensed to the subject on Day 1 of each cycle ([Section 8.2.1](#)).
- z. IP is scheduled to be taken on Day 1 to Day 21 of each cycle, unless there has been a schedule modification of IP administration due to toxicity. As of Amendment 3.0, all subjects in Cycles 1 or 2 will receive CC-486 for 14 days of a 28-day cycle schedule. Subjects may increase to a 21-day schedule at the conclusion of Cycle 2 if there are no Grade 3 or 4 toxicities requiring dose delay or reductions and if there is no evidence of hematological improvement upon discussion and agreement between the investigator and the Medical Monitor. Subjects remaining beyond Cycle 2 will continue to receive 300 mg oral azacitidine or matching placebo QD for 21 days of each 28-day treatment cycle. On ■■■■■ days, IP will be administered by the study site personnel in the clinic. Subject will self-administer all other IP doses in the treatment phase. Antiemetic medication (not supplied by the sponsor) may be administered 30 minutes prior to IP administration at the investigator's discretion ([Section 8.2.2](#)).
- aa. Day 1 of Cycle 2 only.

cc. The type, number of units, reason and date of transfusions are to be collected after randomization and until 28 days after the last dose of IP or until the last study visit, whichever occurs later as detailed in [Section 6.7.1](#).

dd. Assessment of all bleeding events should be performed during the treatment phase starting on Day 1 of Cycle 1, as detailed in [Section 6.7.2](#), and at Treatment Discontinuation. Information for each bleeding event should be recorded on the appropriate CRF.

ee. International Working Group Response/Improvement Assessment is scheduled to be performed on Day 1 of Cycles 3, 6, and 12, and every 6 cycles thereafter (eg, Day 1 of Cycles 18, 24, etc.), and could be done at any time prior to starting the next cycle (eg, prior to starting Cycles 4, 7, 13, etc., respectively) ([Section 6.7.5](#)).

- ff. An assessment of disease status must be performed at the end of Cycle 6, prior to starting Cycle 7.
- If subjects have met any of the following, subjects can continue on to Cycle 7 and beyond, and will be assessed for disease status at the end of every cycle:
 - RBC transfusion independence, or
 - platelet transfusion-independence for those subjects who were platelet transfusion dependent at baseline, or
 - Hematologic Improvement (HI; [Cheson, 2006](#); [Appendix D](#)), or
 - $\geq 50\%$ reduction in average RBC transfusion requirement in the 56-day (8-week) period immediately prior to disease status assessment as compared to the average baseline RBC transfusion requirement, or
 - any other clinical benefit, including no evidence of progressive disease (see [Section 12](#) for definitions of progressive disease).Thereafter, subjects may be discontinued from protocol-prescribed therapy for any of the reasons detailed in [Section 12](#).
 - If subjects have failed to meet any of the above criteria at the end of Cycle 6, subjects will be discontinued from protocol-prescribed therapy ([Section 6.7.6](#)).

The decision to discontinue a subject, which will not be delayed or refused by the sponsor, remains the responsibility of the treating physician. However, prior to discontinuing a subject, the investigator may contact the Medical Monitor and forward appropriate supporting documents for review and discussion.

gg. All subjects discontinued from protocol-prescribed therapy for any reason should be followed for survival and subsequent MDS therapies ([Section 6.7.9](#)).

hh. Following unblinding, subjects could enter the Extension Phase to continue to receive oral azacitidine and/or be followed for survival. See details for EP in [Appendix J](#).

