1.4.1 Risk Assessment

Potential Risk of Clinical Significance	Summary of Data/Rationale for Risk	Mitigation Strategy
Study Intervention - Azacitidine		
Neutropenia and severe infections	In subjects randomized to oral azacitidine 300 mg at 21-day treatment schedule, the most frequent hematological AEs were neutropenia, febrile neutropenia,	To mitigate risk of severe infections, during Cycles 1 and 2 (higher risk period for severe infections) the subjects will receive oral azacitidine for 14 days of a 28-day cycle

Potential Risk of Clinical Significance	Summary of Data/Rationale for Risk	Mitigation Strategy
	
and associated infections. There was an imbalance in incidence of death between the drug and placebo treatment groups. Most of the death cases in the oral azacitidine-treated subjects occurred during the first 56 days on treatment with infections being the leading cause of death. Affected subjects showed lower median ANC at baseline, which could have made them more susceptible for severe infections.
	
schedule. The treatment can be extended to a 21-day schedule after Cycle 2, if a subject did not experience Grade 3 or 4 toxicities requiring dose delay or reductions and if there is no evidence of hematological improvement on 14-day dosing schedule.
 
During the first 2 cycles on treatment subjects' blood counts will be monitored on weekly basis, reducing to biweekly monitoring up to Cycle 12.
 
Guidance for IP dose modification due to toxicities including neutropenia and febrile neutropenia is provided in Section 8.2.4 and Table 2 of the Protocol.
 
A strong recommendation regarding administration of prophylactic fluoroquinolone antibiotics or other recognized prophylactic antibiotics was provided for subjects who develop Grade 4 neutropenia (see Section 9.1).

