4.1.2 Randomization and Double-blind Treatment Phase

Following confirmation of eligibility, subjects will be randomized in a 1:1 ratio to receive oral azacitidine or placebo 300 mg QD for 21 days. Randomization will occur by a central

randomization procedure using Interactive Response Technology (IRT, including an Interactive Voice Response System [IVRS] and an Interactive Web Response System [IWRS]) with stratification as described in [Section 8.3](#). As of Amendment 3.0, all subjects in Cycles 1 or 2 will receive CC-486 for 14 days of a 28-day cycle schedule. Subjects may increase to a 21-day schedule at the conclusion of Cycle 2 if there are no Grade 3 or 4 toxicities requiring dose delay or reductions and if there is no evidence of hematological improvement upon discussion and agreement between the investigator and the Medical Monitor. Subjects remaining beyond Cycle 2 will continue to receive 300 mg oral azacitidine or matching placebo QD for 21 days of each 28-day treatment cycle.

The first dose of IP should be administered within 3 days of randomization and can be on the same day of randomization. After randomization, no crossover between the treatment groups will be permitted during any point of the study.

During the double-blind treatment phase, subjects will ingest IP (oral azacitidine or placebo) once a day on the first 21 days of each 28-day cycle (see [Section 8.2.2](#) for details). Dose modifications may occur for managing toxicity if necessary during treatment ([Section 8.2.4](#)).

Best supportive care may be used in combination with study treatment as deemed necessary. Best supportive care includes, but is not limited to, treatment with RBC transfusions (packed red blood cell [pRBC] or whole blood), single donor or pooled donor platelet transfusions, antibiotic, antiviral and/or antifungal therapy, nutritional support as needed, and granulocyte colony stimulating factors for subjects experiencing neutropenic fever/infections ([Section 9.1](#)). Best supportive care for this study excludes the use of ESAs and other hematopoietic growth factors (granulocyte colony stimulating factors are allowed only for subjects experiencing neutropenic fever/infections as well as for secondary prophylaxis under certain conditions as described in [Section 9.1](#)).

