6 PROCEDURES

All of the required assessments are indicated in [Table 1](#) with an “X” on the visits to be performed. All data obtained from these assessments must be present in the subject’s source documentation. All routine assessments of Cycles 1 and 2 must be performed \pm 3 days of the scheduled day indicated in the table. All routine assessments of Cycles 3 and beyond must be performed \pm 7 days of the scheduled day indicated in the table. However, please note that in all circumstances a drug holiday of 7 days needs to be maintained for the treatment schedules of 300 mg and 200 mg for 21 days /28-day cycle (14 and 21 days, respectively, for modified treatment schedules of 200 mg for 14 days/28-day cycle and 7 days/28 day-cycle. During follow-up, the study visit window is \pm 7 days for visits scheduled monthly (including the follow-up visit 28 days after last dose if necessary) or \pm 14 days for visits scheduled every 3 month. One cycle (one month) is considered as 28 days (ie, 4 weeks). Procedures are described in detail below.

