6.6.5 Hematology and Serum Chemistry Laboratory Evaluations

Hematology and serum chemistry laboratory analyses must be performed according to [Table 1](#). The same parameters as required at screening should be evaluated (see [Section 6.1](#) for details regarding the parameters for hematology and serum chemistry, respectively).

The hematology samples will be collected prior to IP administration and will be analyzed by the central laboratory. The frequency of hematology assessment in the treatment phase is as such: weekly on Day 1, 8, 15 and 22 in Cycles 1-2, and biweekly on Day 1 and 15 in Cycles 3-12, and monthly on Day 1 thereafter and at Treatment Discontinuation.

The serum chemistry samples will be collected prior to IP administration and will be analyzed by the central laboratory. The frequency of serum chemistry assessment in the treatment phase is as such: weekly in Cycles 1-2 and monthly on Day 1 thereafter, and at Treatment Discontinuation.

On a case-by-case basis and at the investigator's discretion, the Day 8, 15, and 22 hematology and serum chemistry draws may be performed at the subject's local/primary physician office and shipped to the central laboratory for analysis or obtained via an in-home nursing service (where

available). In these specific cases, the sponsor needs to be consulted prior to performing these blood draws to assess logistics and obtain local laboratory details. In addition, to ensure the medical care of the individual study subject is maintained, the investigator remains responsible for all subject procedures performed during the study and communication with the subject must be continued. Proper documentation is required in the source documents at the investigative site in these cases.

Any or all laboratory assessments may be repeated more frequently if clinically indicated. In the event that an immediate laboratory assessment is required to acutely manage a subject, local laboratory tests may be used. In addition to collecting the local laboratory sample, a second sample should be collected and sent to the central laboratory.

Refer to [Section 11.3](#) for guidance on abnormal laboratory values and test results.

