8.2.3 Missing Doses

All efforts should be made to administer IP on all of the scheduled days of each 28-day treatment cycle. Any missed doses during that period should not be taken after the last scheduled day of administration, but should be returned by the subject for IP accountability.

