Subjects who have their IP dose reduced or treatment schedule modified may return to their original dose and/or schedule in a step-wise fashion upon discussion and agreement between the investigator and the Medical Monitor provided that the increased dose or treatment schedule is tolerable and at least two additional treatment cycles have occurred since the dose reduction or treatment schedule modification. The treatment schedule should first be increased from 7 to 14 days and then 14 to 21 days, followed by a dose escalation step from 200 to 300 mg.

The dose/treatment schedule modifications steps for 21 days schedule are:

	Dose/schedule		
	300 mg/21d		Level 1
Dose escalation step	200 mg/21d	Dose reduction step	Level -1
Dose escalation step	200 mg/14d	Dose reduction step	Level -2
Dose escalation step	200 mg/7d	Dose reduction step	Level -3

Refer to [Section 8.2.5](#) if, despite the temporary interruption, delay or modification of study treatment, the toxicity persists for more than 42 days and is considered by the investigator to be at least possibly related to study treatment.

Following any modification of study treatment or if a dose is missed, the subject should stay on the visit schedule as specified in [Table 1](#). Unscheduled visits may occur to monitor the subject’s toxicities if necessary.

Dose Modification for Febrile Neutropenia

Any subject who experiences febrile neutropenia \geq Grade 3 will have IP held until fever has resolved; must be afebrile for 3 days before re-starting IP, see [Table 2](#). Administration of antibiotic, antiviral and antifungal therapy is strongly recommended.

Dose Modification for Neutropenia Grade 4

- Grade 4 ANC at Day 1 of a cycle:

Subjects with Grade 4 ANC at Day 1 of a cycle are going to be dosed for a maximum of 14 days on the respective dose level 300 mg or 200 mg or a maximum of 7 days when already on a 14-day dosing schedule. If a subject is stable or improving over several cycles, a discussion with the Medical Monitor is necessary to determine the dose schedule, see [Table 2](#).

- ANC change during a cycle:

Subjects who experience a drop in the ANC during a cycle (e.g. from Grade 3 to Grade 4 or for $> 50\%$ drop for subject with Grade 4 at Day 15 or Day 8 [Day 8 during the 1st two cycles]) will hold the dose for the remaining cycle. If subject is stable or improving for several cycles, a discussion with the Medical Monitor is necessary to determine the dose schedule, see [Table 2](#).

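### In Cycles 3–12 the ± 7-day window lets a compliant Day 15 blood count fall on Day 22, when no dose of a 21-day course is left for the neutropenia hold to stop

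*Protocol*

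**What the plan says.** **Window.** Table 1 footnote a (Protocol Section 5) gives ± "3 days for Cycles 1 and 2; ± 7 days for Cycle 3 and beyond" and allows exceptions for particular assessments. Section 6 repeats the rule: "All routine assessments of Cycles 3 and beyond must be performed" within 7 days either side of the scheduled day. Neither Table 1 footnote q (hematology) nor Section 6.6.5 states an exception.

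**Counts.** After weekly counts in Cycles 1–2, Section 6.6.5 schedules hematology "biweekly on Day 1 and 15 in Cycles 3-12, and monthly on Day 1 thereafter". Section 1.4.1 lists this among its risk mitigations: "reducing to biweekly monitoring up to Cycle 12".

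**Dosing.** On the 21-day schedule IP is taken "once a day on the first 21 days of each 28-day cycle". Section 8.2.3 rules out later catch-up: "Any missed doses during that period should not be taken after the last scheduled day of administration". Footnote a adds that "a drug holiday of 7 days needs to be maintained for the treatment schedules of 300 mg and 200 mg for 21 days".

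**Hold rule.** Section 8.2.4 and Table 2 say that subjects whose neutrophil count drops during a cycle, with examples ending "Day 15 or Day 8 [Day 8 during the 1st two cycles]) will hold the dose for the remaining cycle". Day 8 is confined to the first two cycles, so in a routine cycle from Cycle 3 the scheduled count the rule refers to is Day 15.

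**The concern.** The hold has an effect only if the count arrives while doses remain. On the 21-day schedule seven dosing days remain at Day 15 (Days 15 to 21), and the general window is also seven days. A site can therefore meet every stated timing requirement, draw the Day 15 sample at the late edge, and have given the whole course before a fall to Grade 4 is seen. The monitoring interval that Section 1.4.1 offers as mitigation stretches in the same way. What is at stake is whether two safety provisions, the count and the hold, work together as written in Cycles 3–12.

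**Working it through.** This is day-count arithmetic; no power or alpha figure is involved.

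**Inputs**
- Nominal counts on Days 1 and 15 of a 28-day cycle (Section 6.6.5), so the next Day 1 is Day 29.
- Window *w* = 7 days from Cycle 3 (footnote a, Section 6).
- Last dosing day *L* = 21, 14 or 7, by schedule (Section 8.2.4).
- Sample drawn before that day's dose (Section 6.6.5).

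**The plan's own figure.** 15 − 1 = 14 days and 29 − 15 = 14 days, so the nominal schedule is biweekly as stated.

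**Permitted range for the Day 15 count.** 15 − 7 = Day 8 to 15 + 7 = Day 22.

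**Doses left to hold** = max(0, *L* − day of count + 1).

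| Day of count | 21-day schedule | 14-day schedule | 7-day schedule |
|---|---|---|---|
| 8 | 14 | 7 | 0 |
| 15 (on time) | 7 | 0 | 0 |
| 18 | 4 | 0 | 0 |
| 21 | 1 | 0 | 0 |
| 22 | 0 | 0 | 0 |

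Day 18 is the late edge of the ± 3-day window used in Cycles 1–2. It is shown for scale, not as a proposal. The table allows nothing for turnaround: samples go to the central laboratory, and Section 8.2.5 acknowledges that results take time.

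**Gap between consecutive scheduled counts**
- Day 1 on time, Day 15 count on Day 22: 22 − 1 = 21 days.
- Day 1 sample drawn 7 days early (Day −6, counting Day 0), Day 15 count on Day 22: 22 − (−6) = 28 days. The first 7 of these days precede dosing.
- Day 15 count on Day 8, next Day 1 seven days late (29 + 7 = Day 36): 36 − 8 = 28 days. Days 22 to 35, which is 14 days, are off drug.

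Both 28-day routes respect the 7-day drug holiday.

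**Where the window is not the cause**
- *Shorter schedules.* On the 14-day schedule an on-time Day 15 count follows the last dose; only an early draw (Days 8 to 14) leaves any. On the 7-day schedule no day in the window leaves any. Section 8.2.4 also caps subjects with Grade 4 neutropenia on Day 1 at 14 dosing days, or 7 if already on a 14-day schedule, so its Day 15 test for a further drop meets the same problem unless the Medical Monitor discussion alters the schedule.
- *Cycle 13 onward.* Only Day 1 is scheduled, so the hold has no scheduled mid-cycle count.

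**The case against.** Several stronger readings are tempting, and the documents do not support them.

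- **That the hold fails generally from Cycle 3.** It does not. On the 21-day schedule, counts on Days 8 to 21 leave 14 down to 1 doses. Only the late edge leaves none.
- **That Day 1 + 7 and Day 15 − 7 coincide, so two counts could fall on the same day.** The Day 1 sample precedes dosing, and IP is dispensed only after Day 1 procedures are complete (footnotes q and y, Sections 6.6.5 and 8.2.1). A late Day 1 therefore moves dosing, and Day 15 with it. There is no 0-day gap.
- **That a subject could be on drug for 28 days between counts.** The 28-day gap needs an early Day 1 draw or a late next Day 1, and part of it is off drug.
- **That this window bears on the deaths reported in Section 1.4.1.** That section places most azacitidine-arm deaths in the first 56 days, which is two 28-day cycles. Those cycles have weekly counts and ± 3 days.

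Other points carry weight. The hold rule's examples are introduced as examples, so an unscheduled count could also trigger it, and extra counts are allowed. Weekly counts apply for two cycles after a dose-level change, which arguably covers Cycles 3–4 for subjects moved from 14 to 21 days; a Day 8 count drawn 7 days late then falls on Day 15 and leaves 7 doses. Section 8.2.5 requires hematologic recovery before the next cycle. These soften the consequence, but extra counts are discretionary and the recovery requirement protects only the following cycle.

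It can also be said that sampling before IP administration rules out Day 22. Section 6.6.5 does not write this as a window, and it schedules Day 22 counts in Cycles 1–2, when no dose is due that day.

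Finally, by the January 2019 cut-off all 216 analyzed patients had completed 12 months or stopped treatment, so few now stand to benefit from the Cycle 3–12 wording. That limits the urgency but does not remove the inconsistency.

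**Conclusion.** The point holds in limited form. In Cycles 3–12 the general window applies to the Day 15 hematology sample, and at its late edge the within-cycle hold cannot act on the scheduled count: 7 doses are left on an on-time count and 0 on Day 22 of the 21-day schedule. The scheduled interval can reach 21 days with Day 1 on time, against 14 intended. Separately, the hold rule lacks a usable on-time count on the 14- and 7-day schedules and has no scheduled mid-cycle count from Cycle 13.

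This rests on three assumptions: footnote a and Section 6 mean what they say for hematology, samples are taken before the day's dose, and the cycle is routine, with no recent dose change. Day 22 and the 21- and 28-day gaps are permitted extremes; the documents do not show how often they occurred. It is a correction that should be made to a safety provision, and it is not evidence that the provision failed in practice.

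**What to change.** Reconcile footnote a and Section 6 with Sections 6.6.5, 8.2.4 (with Table 2) and 1.4.1:

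1. Give the Cycle 3–12 hematology sample its own window, separate from the general visit window, so that on the 21-day schedule the count used by the hold rule falls while doses remain. Other assessments can keep ± 7 days.
2. State which count the hold rule refers to on the 14- and 7-day schedules and from Cycle 13. The Extension Phase should be covered too: Appendix J applies Section 8.2.4 but requires, at a minimum, only a blood count before each cycle.

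The width of the window and the clinical rule are for the sponsor to set. Item 1 costs protocol wording and some scheduling freedom for the Day 15 sample, and it adds no scheduled draw. The cost of item 2 depends on how the sponsor resolves it.
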